- Carry out active surveillance with all subjects by visiting house daily for 2 weeks. Measure rectal temperature daily. Use daily form to record symptoms or lack of symptoms. Have physician available at clinic and inform family of subjects that the physician is available should there be any illness during the time of the study. If subjects are brought to the clinic, record all symptoms in patient medical records. These medical records will be the source documents for the passive surveillance.

Day 59, 63, 70, 77 (first 150 subjects only)

- Collection of stool sample for rotavirus antigen by ELISA

Day 71- 83

- Twice weekly active surveillance inquiring about symptoms or illnesses among subjects.

Day 84

- Obtain a serum blood sample for serology.
- Insure that all concomitant medication taken during the study have been recorded.

Day 85 to 6 months after third dose

- Monthly active surveillance to complete 6 months of follow up. With each visit, inquire about symptoms or illnesses among subjects.
- At end of 6 months, terminate subject from the study

Laboratory testing

Fecal samples will be collected as whole stool samples by the parent of the subject or the field worker using a stool cup and taken to the field clinic within 8 hours of passing of the sample. At the clinic, it will be placed in a glass vial with saline (about 10% feces to saline ratio), labelled and placed into a refrigerator (+4°C). Specimens will be transported to the ICDDR,B virology lab within 48 hours and maintained at +4° C until tested. Blood specimens will be obtained by venipuncture (about 3 ml) in clinic using sterile technique. Blood will be placed into a vacutainer without anticoagulants. After blood has clotted, it will be centrifuged and serum transferred to three labelled cryovials (3 aliquots) and frozen at -20° C.

Stool samples, diluted in PBS will be tested for the presence of rotavirus antigen using ELISA (Unicomb et al, 1993; Azim et al., 1999). Stools found to be positive by ELISA will be further characterized by polyacrylamide gel electrophoresis and by reverse-transcriptase-polymerase chain reaction to determine G and P genotype (Unicomb et al., 1999, Gouvea et al., 1990; Gentsch et al., 1992). A sample of the presumptive vaccine strains will be confirmed as vaccine strains at Smith Kline Biologicals using sequencing. Strains of rotavirus will be typed following a scheme described previously (Unicomb et al., 1999). Anti-rotavirus IgA antibody titers will be determined by ELISA using standard methods (Ward, 1989). Serum samples will be available for neutralization assays, though this is not a stated outcome of the study.

Since the ELISA IgA titers are a crucial outcome of the study and since we want to insure that there is agreement between different studies with the vaccine from different countries, but also want to develop our capacity for carrying out a validated assays in Dhaka, we will split the serum samples and have them tested in the laboratory of either [name] or Smith Kline Biologicals where the assay has been validated. [name] has agreed to be a consultant to assist with the standardization of the assay.

Data Safety Monitoring Committee (DSMB)

A committee will be formed including pediatricians to evaluate the reactogenicity data before moving from the older age to the younger age group. The committee will prepare a letter with its recommendations for the file at each stages in the study.

Expected outcomes and timeframe

1. We expect the vaccine to be safe as determined by our adverse event surveillance when given to toddlers and to infants. We expect to detect no cases of intussusception in either group. The vaccine administration may be associated with mild elevations of temperature with a rate significantly higher than control levels, but this mild reactogenicity will not be perceived as clinically important.
2. We expect that most (>70% of infants) will develop a significant increase in serum IgA antirotavirus antibody titer as determined by ELISA and this take rate will be significantly higher than in those receiving the placebo.
3. We expect that the vaccine strain will be detected in a small proportion of fecal specimens of toddlers, but a high proportion of infants when tested 7 days following vaccination. It may still be detected from a few of the infants, when tested 28 days following vaccination.

Following approvals from the appropriate committees and regulatory bodies, we expect Part 1 (the safety studies in toddlers) can be carried out during a 5 month time frame (including information to the community about the study, training of workers, identification of eligible children, setting of a clinic etc). Following collection and analysis of safety data, the Data Safety Monitoring Board will meet to review the safety data. If found sufficiently safe to proceed, the infants in Part 2 can be recruited and vaccinated within about 6 months. Testing the serum specimens for IgA anti-rotavirus antibody will require an additional month. Thus we expect a report summarizing safety and IgA serology can be available within 12-15 months of starting the study, thus preparing the way for a follow-up efficacy study if appropriate. The infants will however be followed for a total of six months after the last dose of vaccine to detect any late adverse events if they were to occur.

Serology will be presented both as the number of infants with 4 fold rises in antibody titer as well as geometric mean titers in the vaccine and placebo groups

Previous experience of the laboratory in the proposed field of research

ICDDR,B scientists have conducted a variety of studies to define the epidemiology and microbiology of rotavirus infections. The Centre also conducted phase II safety and immunogenicity studies with rhesus rotavirus tetravalent vaccines and was prepared to conduct a phase III study with that vaccine when efforts to further evaluate that vaccine were discontinued. The Centre has a long history of studies of prevention of diarrheal diseases including rotavirus as well as cholera, typhoid, shigella, and ETEC. [name] has studied the vaccine based on the HRV strain 89-12 in safety, immunogenicity and efficacy studies in the US.

Facilities Available

Describe the availability of physical facilities at the place where the study will be carried out. For clinical and laboratory-based studies, indicate the provision of hospital and other types of patient's care facilities and adequate laboratory support. Point out the laboratory facilities and major equipments that will be required for the study. For field studies, describe the field area including its size, population, and means of communications. (TYPE WITHIN THE PROVIDED SPACE).

The International Centre for Diarrhoeal Disease Research, Bangladesh (ICDDR,B) has large multi-disciplinary international and national scientific research staff. Existing field, hospital, laboratory and office facilities will be used for this study. ICDDR,B scientists have conducted a variety of vaccine studies including rotavirus.

Field site

The field component of the study will be carried out in urban slums in Mirpur in Dhaka. This site is being used currently for a phase II study of the ETEC vaccine.

Clinical facilities

Sishu hospital is the largest paediatric hospital in Bangladesh. The hospital has the experience and capacity for diagnosis, non-surgical and surgical management of intussusception, and a pediatric surgeon at this hospital is a co-investigator on the protocol to assume responsibility for the care of children suspected of having IS.

Laboratory facilities

Existing laboratory facilities in ICDDR,B will be used.

Data Analysis

Describe plans for data analysis. Indicate whether data will be analyzed by the investigators themselves or by other professionals. Specify what statistical softwares packages will be used and if the study is blinded, when the code will be opened. For clinical trials, indicate if interim data analysis will be required to monitor further progress of the study. (TYPE WITHIN THE PROVIDED SPACE).

Baseline characteristics of the subjects receiving vaccine and placebo will be examined for group comparability. Any significant baseline differences will be controlled for during data analysis. The frequency distribution will be examined to assess the distribution of data. Proportion of infants with adverse events will be compared between the different groups (vaccine, placebo, different doses and viral concentrations). Proportion of subjects that shed rotavirus at different time periods will be compared. Serological measures (proportion with ≥ 4 -fold increase in titer and geometric mean titer) will be compared between different viral concentrations/ doses and placebo recipients.

The proportions will be compared using χ^2 -tests and rate ratios (95% confidence intervals). The geometric mean titers (GMT) will be compared using non-parametric tests. Multivariate analysis will be done to simultaneously adjust for different factors.

Ethical Assurance for Protection of Human Rights

Describe in the space provided the justifications for conducting this research in human subjects. If the study needs observations on sick individuals, provide sufficient reasons for using them. Indicate how subject's rights are protected and if there is any benefit or risk to each subject of the study.

Human rotavirus vaccine (RIX4414), designed for preventing rotavirus will be evaluated among young children since the risk of the disease is greatest in that age group. Infants will be enrolled after their parents have been given a full explanation of the study and they have understood the implications of participating in this study, and have agreed to participate in writing. The study will be conducted according to Good Clinical Practices, the Declaration of Helsinki, and local rules and regulations of Bangladesh and the ICDDR,B.

The investigator and his staff will be aware of the possible increased risk of intussusception and will consider this diagnosis among children presenting symptoms of intussusception. The investigator and his staff will take appropriate actions to evaluate and treat the condition. A child with suspected intussusception will be referred to a local hospital in Dhaka (Children's hospital, Shishu Hospital). The hospital has the experience and capacity for diagnosis, non-surgical and surgical management of intussusception, and a pediatric surgeon at this hospital is a co-investigator on the protocol to assume

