If the evaluation in 2 to 4 years old children reveals no unacceptable reactogenicity and no other concerns about safety, then two and three doses of the study vaccine ($10^{5.0}$ ffu) and two doses of the vaccine ($10^{6.0}$ ffu), administered 1 month apart, will be evaluated in infants 6-14 weeks old. This part will be conducted provided there are no safety concerns in the first study part among toddlers. This will be a safety, and immunogenicity study of two or three doses of the study vaccine when randomized to infants at 6 to 14 weeks of age. Since the second part will aim to identify the most suitable dose of the vaccine for

Bangladesh infants, a larger number of infants will need to be enrolled in order to determine if there is a difference in immune responses between the two doses. Thus a total of 476 infants will be randomised to receive either 2 doses of $10^{5.0}$ ffu (136 subjects), 3 doses of $10^{5.0}$ ffu (136 subjects) or 2 doses of $10^{6.0}$ ffu (136 subjects) or placebo (68 subjects). Safety and reactogenicity assessment will be done through home visits as for the first part. Serum specimens will be collected from all subjects to evaluate IgA antibodies to rotavirus (not serotype specific) by ELISA. Specimens will also be available for neutralization assay against G1, G2, G3, G4, G9, and the vaccine strain, although neutralizing antibodies will not be a primary outcome. Stool samples will be collected from the first 150 enrolled subjects on days 0, 3, 7, 14, 21 after each dose for rotavirus antigen detection to assess vaccine viral shedding.

Routine EPI vaccines should be administered according to local recommendation (at 6, 10 and 14 weeks of age) concomitantly with the study vaccine. The study will form the foundation for conducting Phase III studies of effectiveness and safety in Bangladesh, where we have shown that rotavirus is responsible for substantial public health burden. Ultimately, the goal will be to have available a practical, safe, and effective vaccine for use in prevention of rotavirus morbidity globally.

KEY PERSONNEL (List names of all investigators including PI and their respective specialties)

Name	Professional Discipline/ Specialty	Role in the Project
1. [name]	Epidemiologist (Child Health Programme)	Principal Investigator
2. [name]. [name]	Senior Scientist & Head Matlab HRP	Co-investigator
3. [name] [name]	Epidemiologist & Head (Child Health Programme)	Co-investigator

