Because tetravalent rhesus rotavirus vaccine (Rotashield), licensed in 1998 in the US was associated with intussusception (IS) (Anonymymous, 1999, Murphy et al., 2001), investigations of new rotavirus vaccines must be evaluated for association with IS. The company and the investigators feel that it is unlikely that RIX4414 will lead to IS but this will need to be determined during all clinical trials. The reasons that RIX4414 is unlikely to cause IS includes the following. Wild type rotavirus does not appear to be a cause of IS since the seasonality with rotavirus is so marked in industrialized countries, yet there is no corresponding seasonality for IS. Secondly, RIX4414 is a human strain, typical of the viruses that every child will become infected with early in life, so vaccination does not induce an exposure that would not otherwise occur, unlike administration of rhesus rotavirus vaccine which represented a virus that would not normally infect children. Thirdly, the risk of IS is primarily during the age 4 to 12 months, and we propose completing the vaccination prior to this time period. Nevertheless, all subjects receiving RIX4414 during clinical trials will be informed of the risk of IS, and we will ensure that any potential case of IS is rapidly identified, transported efficiently, diagnosed using state of the art methods, treated with air insufflation when possible and other standard procedure as practised by paediatric surgeons in Dhaka.

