In study part 1, the safety in toddlers will be assessed in a small number of subjects. The purpose of this study is to assess the safety and reactogenicity of the proposed doses of the candidate vaccine when administered orally in a small number of toddlers before clinical development continues in the target population, infants. The safety data collected during the fifteen-day follow-up period (day 0 to day 14) will be reviewed by the medical monitor without breaking the study blind. If there are no safety concerns during this blinded review of the safety data collected, participants in the study part 2 will be vaccinated with the viral concentration of the proposed doses.

Toddlers (2-4 years old) Recruitment, consent, and randomization (1:1:1) with 30 subjects in $10^{5.0}$ ffu (1 dose), 30 subjects in $10^{6.0}$ ffu (1 dose) and 30 in placebo group.	One dose of vaccine or placebo, with surveillance for adverse events (by home visits) and fecal excretion of virus
---	--

Part 2 (Double-blind safety and immunogenicity assessment in infants)

In study part 2, the safety and immunogenicity of the candidate vaccine will be assessed in the target age group - infants approximately 6 weeks of age. Escalating doses (viral concentrations of 10^5 ffu and 10^6 ffu) will be evaluated. All infants will receive by co-administration the recommended EPI vaccines at 6-10-14 weeks, including OPV.

Infants (6-14 weeks old) Recruitment, consent, and randomization (2:2:2:1) with 136 subjects in $10^{5.0}$ ffu (2 doses), 136 subjects in $10^{5.0}$ ffu (3 doses), 136 subjects in $10^{6.0}$ ffu (2 doses) and 68 in placebo group.
	
Two/three doses of vaccine or placebo, 4 weeks apart, with surveillance for adverse events (by home visits) and blood sampling at each study visit for antibody titer changes. Fecal excretion of virus in the first 150 enrolled subjects.

---	---

The investigator and his staff will be aware of the possible increased risk of intussusception and will consider this diagnosis among children presenting symptoms of intussusception. Symptoms consistent with intussusception are severe colicky abdominal pain, persistent vomiting, bloody stools, abdominal bloating and fever up to 41°C. The investigator and his staff will take appropriate actions to evaluate and treat the condition.

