Inclusion criteria for enrollment: Male or female, between 24 months and 48 months of age at the time of the first dose of vaccine for participation in the study part assessing the vaccine in toddlers. Male or female, between 6 and 14 weeks of age at the time of the first dose of vaccine for participation in the study part assessing the immunogenicity and safety of the vaccine in infants. Written informed consent, free of chronic or serious medical condition as determined by history and physical exam within 3 days of the first dose of vaccine, plan to stay in community for at least 3 months.

Exclusion criteria for enrollment: Malnutrition (<-2Z score weight for age), fever (>38°C), acute or chronic illness, use of antimicrobial drug within previous 14 days, hypersensitivity to any of the vaccine components (vaccine composition in **annex III**), use of any investigational drug during previous 30 days, any uncorrected congenital malformation of the gastrointestinal tract, use of any immunosuppressing drugs during the last 14 days (likelihood is remote), any evidence by physical exam of immunosuppressing condition, administration of gamma globulin or any other blood product, previous intussusception or abdominal surgery, known pregnant person in the home.

Elimination criteria during study: If an exclusion criteria develops while participating in the study, the subject will be eliminated from the study.

Definitions:

Fever: Rectal temperature > 38°C

Diarrhoea: Three or more looser stools than normal stools in a 24 hour period.

Contraindications to vaccination: Not applicable.

Conduct of the study: The study will be conducted according to Good Clinical Practices, the Declaration of Helsinki, and local rules and regulations of Bangladesh and the ICDDR,B. It will be reviewed and approved by the Ethical Review Committee (ERC) of the ICDDR,B prior to starting the study. The ERC is a recognized committee for review of research protocols involving humans and has a Multiple Project Assurance (MPA) with a US agency (USAID).

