- On day 42, insure that all concomitant medication taken during the study have been recorded.

Day 43 to 6 months.

- Monthly active surveillance to complete 6 months of followup. With each visit, inquire about symptoms or illnesses among subjects.
- At end of 6 months, terminate subject from the study

For infants(Part 2)

Day 0 (Visit 1)

- Same procedures as performed for toddlers in part 1.
- Obtain a blood sample for serology
- Prepare study vaccine and administer dose 1
- Collection of stool sample for rotavirus antigen by ELISA

Day 3, 7, 14, and 21 (first 150 subjects only)

- Collection of stool sample for rotavirus antigen by ELISA

Day 1-day 27

- Carry out active surveillance with all subjects by visiting house daily for 2 weeks and thereafter twice weekly. Measure rectal temperature daily. Use daily form to record symptoms or lack of symptoms. Have physician available at clinic and inform family of subjects that the physician is available should there be any illness during the time of the study. If subjects are brought to the clinic, record all symptoms in patient medical records. These medical records will be the source documents for the passive surveillance.

Day 28

- Insure that subject is eligible for dose 2 according to inclusion and exclusion criteria
- Obtain a serum blood sample for serology
- Prepare study vaccine and administer dose 2
- Collection of stool sample from subjects (first 150 only) for rotavirus antigen by ELISA

Day 29 – day 42

- Carry out active surveillance with all subjects by visiting house daily for 2 weeks. Measure rectal temperature daily. Use daily form to record symptoms or lack of symptoms. Have physician available at clinic and inform family of subjects that the physician is available should there be any illness during the time of the study. If subjects are brought to the clinic, record all symptoms in patient medical records. These medical records will be the source documents for the passive surveillance.

Day 31, 35, 42, 49 (first 150 subjects only)

- Collection of stool sample for rotavirus antigen by ELISA

Day 43-day 55

- Twice weekly active surveillance inquiring about symptoms or illnesses among subjects.

Day 56

- Insure that subject is eligible for dose 3 according to inclusion and exclusion criteria

- Obtain a serum blood sample for serology
 - Prepare study vaccine and administer dose 3
 - Collection of stool sample from subjects (first 150) for rotavirus antigen by ELISA
- Day 57-day 70

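### Entry up to 14 weeks of age lets vaccine doses fall after 4 months, contrary to the protocol's own intussusception argument; the fixed 6-10-14 week EPI statement also fails for later entrants

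*Protocol*

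**What the plan says.** The Background section of the protocol gives three reasons why the candidate vaccine is unlikely to cause IS. The third is that "the risk of IS is primarily during the age 4 to 12 months, and we propose completing the vaccination prior to this time period". An external referee's opinion bound with the protocol repeats this as a feature of the study.

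The age rule for Part 2, under Inclusion criteria for enrollment, is "between 6 and 14 weeks of age at the time of the first dose of vaccine". The Part 2 overview specifies "Two/three doses of vaccine or placebo, 4 weeks apart", and the project summary has doses "administered 1 month apart, will be evaluated in infants 6-14 weeks old". The day-by-day infant schedule puts dose 1 on day 0, dose 2 on day 28 and dose 3 on day 56. At the last of these the instruction is "Insure that subject is eligible for dose 3 according to inclusion and exclusion criteria", but the only age criterion refers to the first dose.

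On routine vaccines, the Part 2 overview says: "All infants will receive by co-administration the recommended EPI vaccines at 6-10-14 weeks, including OPV". The same paragraph describes the target group as "infants approximately 6 weeks of age", and the rationale in the Background speaks of vaccinating at 6-8 weeks. Neither of these narrower ages is the entry criterion.

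**The concern.** The IS argument states a property of the design: that the course is over before the main risk period begins. An entry range eight weeks wide, followed by a course of up to eight weeks, does not guarantee this. Committees that weigh the risk of the trial may rely on the statement, and one referee evidently did, so it should be true of the trial as written.

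The EPI statement is a separate matter and plays no part in the IS argument. It fixes three ages for every infant, although infants may enter at any point in the range. Early dosing with maternal antibody present, and possible OPV interference, are two of the four reasons the Background gives for testing several doses and concentrations. A reader will want to know which infants were in fact dosed on the EPI schedule.

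**Working it through.** **Inputs (all from the protocol).** Entry age e from 6 to 14 weeks (Inclusion criteria); doses on days 0, 28 and 56 (infant schedule); risk period from 4 months (Background); 136 infants in the three-dose arm and 2 × 136 = 272 in the two two-dose arms, 408 vaccinees in all (Part 2 overview). The protocol does not say at which visits the two-dose arms receive their vaccine; days 0 and 28 are assumed.

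**Conversion.** One month = 365.25/12/7 = 4.348 weeks, so 4 months = 17.39 weeks.

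**Age at each dose.** Age at dose k = e + 4(k − 1) weeks.

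| Entry | Dose 2 | Dose 3 |
|---|---|---|
| 6 weeks | 10 weeks (2.3 months) | 14 weeks (3.2 months) |
| 8 weeks | 12 weeks (2.8 months) | 16 weeks (3.7 months) |
| 10 weeks | 14 weeks (3.2 months) | 18 weeks (4.1 months) |
| 14 weeks | 18 weeks (4.1 months) | 22 weeks (5.1 months) |

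The protocol's stated limit, completion before 4 months, is therefore met at the lower end of the entry range and not at the upper end.

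**Latest entry that meets the limit.** Three doses: 17.39 − 8 = 9.39 weeks. Two doses: 17.39 − 4 = 13.39 weeks. If 4 months is counted as 16 weeks, these become 8 and 12 weeks.

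**Other readings.** With one-month intervals, entry at 14 weeks puts dose 3 at 14 + 2 × 4.348 = 22.7 weeks. If 14 weeks runs to 14 weeks 6 days, it is 14.86 + 8 = 22.9 weeks. No reading satisfies the statement over the whole entry range.

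**How many infants.** The protocol gives no distribution of entry age, so any share is an assumption.

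- All entering by 8 weeks: dose 3 by 16 weeks, so 0% are dosed after 4 months.
- Uniform over 6-14 weeks: three-dose arm (14 − 9.39)/8 = 58%, about 78 of 136; two-dose arms (14 − 13.39)/8 = 7.6%, about 21 of 272; together 99/408 = 24%.
- Uniform over 6-14 weeks, with 4 months as 16 weeks: (14 − 8)/8 = 75% of 136 = 102, and (14 − 12)/8 = 25% of 272 = 68; together 170/408 = 42%.
- Uniform over 10-14 weeks: all 136 three-dose infants, and (14 − 13.39)/4 = 15% of 272, about 41; together 177/408 = 43%.

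**EPI ages.** The doses e, e + 4 and e + 8 coincide with 6, 10 and 14 weeks only when e = 6. Entry at 10 weeks matches two of the three ages (10 and 14), entry at 14 weeks matches one, and entry at 8 or 12 weeks matches none exactly.

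**The case against.** The Background sentence is one of several hedged arguments. The same paragraph says that the IS question must be settled in the trials. Surveillance, referral and DSMB review of IS cover every infant and do not depend on the age argument. The Background also gives a looser limit, completion before 6 months (26.1 weeks), and 22 weeks satisfies it. All of this stands and limits the consequence, but none of it makes the 4-month statement true of the permitted entry range.

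It is also fair that the statement holds for much of the trial: for entry up to about 13.4 weeks in two of the three vaccine arms, and for everyone if recruitment keeps to the 6-8 weeks of the rationale. A reader might take 58% as the share of all infants affected. It applies only to the three-dose arm, under an assumed uniform entry age.

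A reader might also infer that each arm will mix doses given with and without OPV. The protocol does not show this. It says that all infants receive EPI vaccines by co-administration, and a late entrant's EPI course could be moved to the study visits. Only the literal ages would then fail. Mixing is possible but not established.

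Nor can it be said that parents are given the 4-month argument, because the consent text is not available for review. Subgroup analyses by age or OPV are detail for the SAP and are no omission here.

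**Conclusion.** The point holds as an internal contradiction. The protocol claims that vaccination ends before the 4-12 month risk period, while its entry rule and schedule allow dose 2 as late as 18 weeks and dose 3 as late as 22 weeks, with no later age limit. These ages follow from the protocol's own figures. The share of infants affected does not: it is 0% if all enter by 8 weeks, about 24% of vaccinees under uniform entry over 6-14 weeks, and higher with later entry.

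The EPI statement fails separately and more simply: it can be met at all three ages only for entry at about 6 weeks.

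This does not show that the trial carries an increased risk of IS, only that one stated reason for expecting a low risk is not secured by the design. Randomisation protects the between-arm comparisons from the spread in entry age, and no sample size, power or error rate changes. It should be settled before Part 2 starts.

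**What to change.** Before Part 2, reconcile the IS argument and the age rationale in the Background, the Part 2 overview, the inclusion criteria and the infant visit schedule. There are two ways. Either the entry age and schedule are made consistent with the statements, or the 4-month statement is withdrawn from the risk rationale (and from the parent information, if it appears there) and the EPI statement is corrected to describe what later entrants will receive. Which of these is right is the sponsor's clinical decision.

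In either case, record age and OPV co-administration (yes/no) at each dose, so that results can be described for infants actually dosed on the EPI schedule.

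The cost is protocol wording and at most two case report form fields per dose, both known at the visit. If the sponsor chose a narrower entry age, recruitment would be slower.
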